5.1 Imputation rules

5.1.1 Study drug

Missing/partial start date or end date of study drug will not be imputed.

5.1.2 AE date imputation

5.1.2.1 AE end date imputation

Rules for imputing AE end dates are stated below. Date of last contact in the study has been defined as in [Section 2.1.1](#).

1. If the AE end date month is missing, the imputed end date should be set to the earliest of the (date of last contact, 31DECYYYY, date of death).
2. If the AE end date day is missing, the imputed end date should be set to the earliest of the (date of last contact, last day of the month, date of death).
3. If AE year is missing or AE is ongoing, the end date will not be imputed.

5.1.2.2 AE start date imputation

Rules for imputing the AE start date:

The following table explains the notation used in the logic matrix. Please note that **missing start dates** will not be imputed.

	Day	Month	Year
Partial Adverse Event Start Date	Not used	MON	YYYY
Treatment Start Date	Not used	TRTM	TRTY

The following matrix explains the logic behind the imputation.

	MON MISSING	MON < TRTM	MON = TRTM	MON > TRTM
YYYY MISSING	(1) No convention	(1) No convention	(1) No convention	(1) No convention
YYYY < TRTY	(2.a) Before Treatment Start	(2.b) Before Treatment Start	(2.b) Before Treatment Start	(2.b) Before Treatment Start
YYYY = TRTY	(4.a) Uncertain	(4.b) Before Treatment Start	(4.c) Uncertain	(4.c) After Treatment Start
YYYY > TRTY	(3.a) After Treatment Start	(3.b) After Treatment Start	(3.b) After Treatment Start	(3.b) After Treatment Start

Before imputing AE start date, find the AE start reference date.

1. If the imputed AE end date is complete and the imputed AE end date < treatment start date then AE start reference date = min(informed consent date, earliest visit date).
2. Else AE start reference date = treatment start date

Impute AE start date -

1. If the AE start date year value is missing, the date uncertainty is too high to impute a rational date. Therefore, if the AE year value is missing, the imputed AE start date is set to NULL.
2. If the AE start date year value is less than the treatment start date year value, the AE started before treatment. Therefore:
 - a. If AE month is missing, the imputed AE start date is set to the mid-year point (01JulYYYY).
 - b. Else if AE month is not missing, the imputed AE start date is set to the mid-month point (15MONYYYY).
3. If the AE start date year value is greater than the treatment start date year value, the AE started after treatment. Therefore:
 - a. If the AE month is missing, the imputed AE start date is set to the year start point (01JanYYYY).
 - b. Else if the AE month is not missing, the imputed AE start date is set to the later of (month start point (01MONYYYY), AE start reference date + 1 day).
4. If the AE start date year value is equal to the treatment start date year value:
 - a. And the AE month is missing the imputed AE start date is set to the AE reference start date + 1 day.
 - b. Else if the AE month is less than the treatment start month, the imputed AE start date is set to the mid-month point (15MONYYYY).
 - c. Else if the AE month is equal to the treatment start date month or greater than the treatment start date month, the imputed AE start date is set to the later of (month start point (01MONYYYY), AE start reference date + 1 day).

If complete imputed AE end date is available and the imputed AE start date is greater than the imputed AE end date, then imputed AE start date should be set to the imputed AE end date.

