Safety summaries (tables, figures) include data from the pre-treatment period (to display the baseline status e.g. for ECG) and the on-treatment period. Data from the post-treatment period with the exception of deaths should not be included unless requested from Health Authorities or external committees.

In particular, summary tables for adverse events (AEs) will summarize only on-treatment events, with a start date during the on-treatment period, the so-called **treatment-emergent** AEs.

However, all safety data (including those from the post-treatment period) will be listed and those collected during the pre-treatment and post-treatment period are to be flagged.

Visit remapping and assessment windows

If a scheduled visit did not occur, then the data from the treatment discontinuation or study discontinuation visit may be used as the data from the scheduled visit. This is done if the treatment discontinuation or study discontinuation visit occurred closer to the planned study day of the missing scheduled visit than to the planned study day of any other scheduled visit. In this case the treatment discontinuation or study discontinuation visit will be treated as the scheduled visit for the purpose of all analyses so that no missing data imputation will be necessary. Otherwise the data from any scheduled visit that did not occur will be dealt with like any other missing data. If the treatment discontinuation or study discontinuation visit is not re-mapped to any scheduled visit, it will be treated as an unscheduled visit that does not appear in by-visit summaries.

Last contact date

The maximum of the date of last visit, date of last epoch completion, date of withdrawal of consent would be the date of last contact for the patient participating in the study.

The last contact date is defined as the latest complete date from the above list or the cut-off date whichever comes first. The cut-off date will not be used for last contact date, unless the patient was seen or contacted on that date. No date post cut-off date will be used. Completely imputed dates (e.g. the analysis cut-off date programmatically imputed to replace the missing end date of a dose administration record) will not be used to derive the last contact date.

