2.8.1 Adverse events (AEs)

Adverse events after informed consent including asthma exacerbations will be listed.

Adverse events starting on or after the day of the first intake of study drug and until 7 days after the last intake of study drug will be classified as treatment emergent adverse events. Adverse events that started during the study after informed consent and before the day of the first intake of study drug will be classified as prior adverse events and not included in tabulations of treatment emergent adverse events.

The number and percentage of patients who reported TEAEs will be summarized by primary system organ class (SOC), preferred term (PT), and treatment group for

- all adverse events (AEs)
- all AEs by maximum severity
- AEs suspected to be related to study drug
- AEs by standardized MedDRA query (SMQ) level serious AEs (SAEs)
- AEs leading to permanent study drug discontinuation
- Serious adverse events

Unless otherwise specified, primary system organ classes will be sorted alphabetically and, within each primary system organ class, the preferred terms will be sorted in descending order of frequency in the QAW039 150 mg once daily treatment group. If a patient reported more than one AE with the same preferred term, the AE will be counted only once. If a patient reported more than one AE within the same primary system organ class, the patient will be counted only once at the system organ class level.

In addition, the most frequent AEs will be presented by preferred term in descending order of frequency in the QAW039 150 mg once daily treatment group.

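### An adverse event with no recorded start year gets a NULL start date and so enters no treatment-emergent table; the SAP should give it a cautious default

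*SAP*

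**What the plan says.** SAP 5.1.2.2 opens by noting that missing AE start dates "will not be imputed". It then sets out a matrix by start year and month relative to treatment start. Where the year is missing, the matrix offers no rule for any month, and rule 1 says: "Therefore, if the AE year value is missing, the imputed AE start date is set to NULL". The reason given is that the date is too uncertain.

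Other incomplete dates are resolved:

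- Rule 4.a, start year equal to the treatment-start year and month unknown: "And the AE month is missing the imputed AE start date is set to the AE reference start date + 1 day".
- Rule 4.c, same year and month equal to or after the treatment-start month: "the imputed AE start date is set to the later of (month start point (01MONYYYY), AE start reference date + 1 day").
- Before these rules are applied, the section fixes an AE start reference date. It is treatment start, unless the complete imputed end date is before treatment start; then it is the earlier of consent and first visit.

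Classification rests on the start date. SAP 2.8.1 defines treatment-emergent AEs as those "starting on or after the day of the first intake of study drug and until 7 days after the last intake of study drug". Prior AEs are "Adverse events that started during the study after informed consent and before the day of the first intake of study drug". SAP 2.1.1 adds that AE summary tables "will summarize only on-treatment events, with a start date during the on-treatment period". All safety data are listed (SAP 2.8), and deaths after first dose are tabulated separately (SAP 2.8.2).

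**The concern.** A NULL start date satisfies neither the treatment-emergent nor the prior definition, and no section says what happens to such an event. Read as written, it drops out of the treatment-emergent tables: all AEs, severity, relatedness, discontinuation and serious AEs (SAP 2.8.1), events of special interest (SAP 2.8.1.1) and the disclosure tables (SAP 2.8.1.2). SAP 2.8 promises selected tables for all data after first intake, but these too need a date to place the event after first intake.

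The usual safety convention is to count an event of uncertain onset rather than omit it, and rules 4.a and 4.c follow that convention. Rule 1 does the reverse. What is at stake is the completeness of the safety tables, mainly for rare terms such as the idiosyncratic reactions in Protocol Table 16-1, where one case can matter.

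**Working it through.** There is no plan figure to reproduce. The check applies the rules of SAP 5.1.2.2, then the classes of SAP 2.8.1, to one example of each kind of partial date.

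**Assumed dates (illustrative only).** Treatment start 10 Jun 2019; consent 42 days earlier, 29 Apr 2019; last dose 363 days after treatment start, 7 Jun 2020. The treatment-emergent window of SAP 2.8.1 then runs from 10 Jun 2019 to 14 Jun 2020.

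| Recorded information | Rule | Imputed start | Class |
|---|---|---|---|
| Year missing, ongoing | 1 | NULL | none |
| Year missing, ended 1 Sep 2019 | 1 | NULL | none |
| Year missing, month September, ongoing | 1 | NULL | none |
| 2018, month missing | 2.a | 1 Jul 2018 | before first dose |
| November 2018 | 2.b | 15 Nov 2018 | before first dose |
| 2020, month missing | 3.a | 1 Jan 2020 | treatment-emergent |
| March 2020 | 3.b | 1 Mar 2020 | treatment-emergent |
| 2019, month missing, ongoing | 4.a | 11 Jun 2019 | treatment-emergent |
| 2019, month missing, ended 30 May 2019 | 4.a | 30 Apr 2019 | prior |
| May 2019 | 4.b | 15 May 2019 | before first dose |
| June 2019 | 4.c | 11 Jun 2019 | treatment-emergent |
| August 2019 | 4.c | 1 Aug 2019 | treatment-emergent |

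Only the three missing-year rows are left without a class. A known month or a known end date does not change that. In the third row the month in fact settles the year: between consent (29 Apr 2019) and the end of 2 weeks of follow-up (21 Jun 2020) there is only one September, and it falls on treatment.

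**How uncertain is a missing year?** Protocol 7.1 counts an AE only after consent, so onset is bounded below. Take consent at the screening visit, screening of 2 weeks and a run-in of 4 or 10 weeks (Protocol 3.1). The pre-treatment window is then 6 to 12 weeks. For a 52-week completer the treatment-emergent window is 52 + 1 = 53 weeks, and 1 week of follow-up remains after it. If the event rate is constant (an assumption), the chance that an undated AE is treatment-emergent is:

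- short run-in: 53/(6 + 53 + 1) = 53/60 = 88%
- long run-in: 53/(12 + 53 + 1) = 53/66 = 80%

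SAP section 4 says the study was terminated early, so many patients have shorter exposure. With D weeks of treatment, treatment-emergent is the likelier class when D + 1 exceeds the other windows, 7 to 13 weeks, that is, when D exceeds about 6 to 12 weeks.

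**Scale.** Planned arm size is 669/3 = 223. One patient is 1/223 = 0.45 percentage points.

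**The case against.** Rule 1 is a deliberate convention with a stated reason. In rule 4.a the year is known, so different treatment of a wholly unknown year is coherent. No sentence in the SAP says that NULL-start events are excluded; that is inferred. Missing years should be rare: AEs are sought at every visit with start and end dates (Protocol 7.1), SAEs are reported within 24 hours of the site learning of them (Protocol 7.2.2), SAE documentation is fully source-verified (Protocol 8.1), and missing values are queried (Protocol 8.3).

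Much of this stands. The affected events are probably very few, none is lost from the listings, and deaths are tabulated by time of death. But the exclusion is the only reading the definitions allow. The uncertainty argument is weak, since consent bounds the onset. The SAP does not treat a missing year as beyond imputation elsewhere either: the concomitant-medication rules (SAP 5.1.3.2, rule 1) impute a start date in that situation.

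A reader might infer more than the documents support:

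- That undated events tend to be serious ones. Nothing in the documents says so, and the SAE procedures above point the other way.
- That seriousness, or an end date during treatment, shows onset on treatment. Seriousness says nothing about timing, and an event that ends on treatment may have begun in the run-in.
- That every less incomplete date is placed on treatment. Rules 2.a, 2.b and 4.b place events before first dose, and so does rule 4.a when the event ended before treatment.

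**Conclusion.** The point holds, and it is minor. As written, an AE with missing start year is neither treatment-emergent nor prior and enters no treatment-emergent AE or SAE table. This rests on SAP 2.1.1 and 2.8.1 being applied literally, with no unwritten programming default. The direction is non-conservative, and it differs from the section's own handling of uncertain onsets in rule 4.a and in rule 4.c for the same month.

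The effect on this trial cannot be quantified: the number of affected events is not in the documents, is probably very small, and could be zero. The 0.45 percentage points is only what one patient represents at the planned arm size, not an estimate of bias. Actual arm sizes after early termination are not given; smaller arms would make it larger. The 80% to 88% range depends on a constant event rate and full exposure, and serves only to show that NULL sets aside what is usually the likelier class.

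**What to change.** Replace rule 1 with a classification rule. If the start year is missing, count the AE as treatment-emergent unless (a) its complete or imputed end date is before first dose, in which case it is prior, or (b) other recorded information, such as a known month, shows onset before first dose or more than 7 days after last dose. If programming needs a date, use the AE start reference date plus one day, keep the section's existing cap at the end date, and flag the date as imputed in the listings. Amend the opening note of SAP 5.1.2.2 to match.

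In the example above, the ongoing event and the one that ended on 1 Sep 2019 would both start on 11 Jun 2019 and count as treatment-emergent. A missing-year event that ended on 30 May 2019 would start on 30 Apr 2019 and be prior.

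The cost is a few lines of SAP text and code. The downside is that an occasional pre-treatment or post-treatment event with no usable dates is counted as treatment-emergent. That includes any event whose end year is also missing, because SAP 5.1.2.1 does not impute that end date. SAEs are collected to 30 days after last dose (Protocol 7.2.2), so late onsets are possible. The imputed day-2 onset is a placeholder and should not be used in any time-to-onset summary.

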5.1.3 Prior and Concomitant medication date imputation

5.1.3.1 Concomitant medication end date imputation

Rules for imputing the CM end date are stated below. Date of last contact in the study has been defined as in [Section 2.1.1](#). Concomitant medication end dates will not be imputed for ongoing records.

1. If CM end day is missing and CM month/year are non-missing then impute CM day as the minimum of date of last contact and the last day of the month.
2. If CM end day/month are missing and CM year is non-missing then impute CM day as the minimum of date of last contact and the end of the year (31DECYYYY).
3. If CM day/month/year is missing then use the date of last contact + 1 day as the imputed CM end date.
4. If imputed CM end date is less than the CM start date, use the CM start date as the imputed CM end date.

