2.1 Data analysis general information

The final efficacy analysis will be performed by Novartis or a designated CRO. The most recent version of SAS or R software will be used to perform all data analyses and to generate tables, figures and listings.

Data included in the analysis

The analysis cut-off date for the primary analysis of study data will be established after all randomized patients have completed 52 weeks of treatment or have discontinued study, or study

terminated by sponsor. All statistical analyses will be performed using all data collected in the database up to the data cutoff date. All data with an assessment date or event start date (e.g. vital sign assessment date or start date of an adverse event) prior to or on the cut-off date will be included in the analysis. Any data collected beyond the cut-off date will not be included in the analysis and will not be used for any derivations.

All events with start date before or on the cut-off date and end date after the cut-off date will be reported as 'continuing at the cut-off date'. The same rule will be applied to events starting before or on the cut-off date and not having documented end date. This approach applies, in particular, to adverse event and concomitant medication reports. For these events, the end date will not be imputed and therefore will not appear in the listings.

General analysis conventions

Pooling of center: Unless specified otherwise, data from all study centers will be pooled for the analysis. Due to expected small size of centers, no center effect will be assessed.

Qualitative data (e.g., gender, race, etc.) will be summarized by means of contingency tables by treatment group; a missing category will be included as applicable. Percentages will be calculated using the number of patients in the relevant population or subgroup as the denominator.

Quantitative data (e.g., age, body weight, etc.) will be summarized by appropriate descriptive statistics (i.e. mean, standard deviation, median, minimum, and maximum) by treatment group.

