2.4.2 Prior, concomitant and post therapies

Medications started and stopped prior to study drug and taken concomitantly will be summarized by treatment group in separate tables in the SAF. The medication will be classified into “prior”, “concomitant” based on the start/end dates.

Prior: Any medication with a start date before Day 1.

Concomitant: Any medication with end date on or after Day 1 or ongoing at the end of trial or missing end date and start date before the end of the Treatment Epoch.

Medications can be considered both prior and concomitant.

Concomitant therapies will be recorded and summarized separately for asthma related medications and other medications. Concomitant therapies will be recorded and summarized separately for asthma related medications and other medications. Concomitant asthma related medications will be summarized by pre-defined category. Concomitant medications not related to asthma will be summarized by pharmacological (ATC) class and preferred term. More than one ATC class per medication is possible and the medication will be reported under all applicable classes.

Short acting beta2 agonist (SABA) rescue medication usage (mean number of puffs) during the screening/run-in period will be summarized. Patients taking prohibited concomitant medications will be noted in the summary of protocol deviations.

All summaries will be by treatment group on the Safety Set.

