The total systemic corticosteroid dose in mg prednisone/prednisolone (or equivalent) over 52 weeks of treatment will be analyzed using the Wilcoxon-Mann-Whitney rank sum test (Van Elteren test). For overall population analysis will be stratified by randomization stratum – blood eosinophils levels (≥ 250 cells/ μl and < 250 cells/ μl). For subgroup with blood eosinophils ≥ 250 cells/ μl , analysis will not include stratification factor. The summary statistics for total SCS dose by treatment group will be provided.

The primary estimand will quantify the treatment effect based on on-treatment data. The total SCS dose data will be aggregated into monthly data for analysis. The primary estimand will account for different post-randomization events as follows:

- Use of rescue medications: Efficacy data collected during use of rescue medication will be used for analysis.

- Early discontinuation of study drug (prior to completing 52 weeks of treatment period): For the patients discontinuing study drug early, the total SCS dose for 52 weeks will be obtained as annualized SCS dose. For example if patient took 280 mg for 7 months then for 12 months patient will be taking $280 \times 12/7 = 480$ mg total SCS dose.
- Use of biologics prior to discontinuation of treatment: Efficacy data collected during the use of biologics will be set to missing, since use of biologics can confound efficacy data. Biologics are usually taken for long period of time. Thus, after replacing SCS dose with missing, patient will not have data available for remaining duration of the study. The total SCS dose will be obtained as annualized dose as explained above.

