2.7.3 Handling of missing values/censoring/discontinuations

No imputation will be done for secondary endpoints.

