5.1.3.2 Concomitant medication start date imputation

Rules for imputing the CM start date:

The following table explains the notation used in the logic matrix. Please note that missing start dates will not be imputed.

	Day	Month	Year
Partial CMD Start Date	Not used	MON	YYYY
Treatment Start Date	Not used	TRTM	TRTY

The following matrix explains the logic behind the imputation.

	MON MISSING	MON < TRTM	MON = TRTM	MON > TRTM
YYYY MISSING	(1) Uncertain	(1) Uncertain	(1) Uncertain	(1) Uncertain
YYYY < TRTY	(2.a) Before Treatment Start	(2.b) Before Treatment Start	(2.b) Before Treatment Start	(2.b) Before Treatment Start
YYYY = TRTY	(4.a) Uncertain	(4.b) Before Treatment Start	(4.a) Uncertain	(4.c) After Treatment Start
YYYY > TRTY	(3.a) After Treatment Start	(3.b) After Treatment Start	(3.b) After Treatment Start	(3.b) After Treatment Start

1. If the CM start date year value is missing, the imputed CM start date is set to one day prior to treatment start date.
2. If the CM start date year value is less than the treatment start date year value, the CM started before treatment. Therefore:
 - a. If the CM month is missing, the imputed CM start date is set to the mid-year point (01JulYYYY).
 - b. Else if the CM month is not missing, the imputed CM start date is set to the mid-month point (15MONYYYY).
3. If the CM start date year value is greater than the treatment start date year value, the CM started after treatment. Therefore:
 - a. If the CM month is missing, the imputed CM start date is set to the year start point (01JanYYYY).
 - b. Else if the CM month is not missing, the imputed CM start date is set to the month start point (01MONYYYY).
4. If the CM start date year value is equal to the treatment start date year value:
 - a. And the CM month is missing or the CM month is equal to the treatment start date month, then the imputed CM start date is set to one day prior treatment start date.
 - b. Else if the CM month is less than the treatment start date month, the imputed CM start date is set to the mid-month point (15MONYYYY).

- c. Else if the CM month is greater than the treatment start date month, the imputed CM start date is set to the month start point (01MONYYYY).

If complete imputed CM end date is available and the imputed CM start date is greater than the (imputed) CM end date, then imputed CM start date should be set to the (imputed) CM end date.

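### Could the SAP's partial-date rules for concomitant medication inflate the primary systemic corticosteroid total?

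*SAP*

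**What the plan says.** SAP 5.1.3.1 completes medication end dates in three tiers. With the day missing, the rule is to "impute CM day as the minimum of date of last contact and the last day of the month". With day and month missing, it is the earlier of last contact and 31 December. With nothing recorded: "If CM day/month/year is missing then use the date of last contact + 1 day as the imputed CM end date". The only exemption is for ongoing records.

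SAP 5.1.3.2 handles start dates. If the month is missing or equals the treatment-start month, "then the imputed CM start date is set to one day prior treatment start date". A later month in the treatment-start year, or any known month in a later year, goes to the first of that month.

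The one use the SAP states for such dates is in 2.4.2, where medications are classed as prior or concomitant "based on the start/end dates".

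On the primary endpoint, SAP 2.5.2 says: "The total SCS dose data will be aggregated into monthly data for analysis". It adds on-treatment data, annualisation after early discontinuation, and exclusion of data collected during biologic use. It names no source for mg and no partial-date rule. For secondary endpoints, SAP 2.7.3 says: "No imputation will be done for secondary endpoints".

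For concomitant medications with no documented end date, SAP 2.1 reports them as continuing at cut-off: "For these events, the end date will not be imputed and therefore will not appear in the listings".

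**The concern.** An on-treatment total aggregated by month depends on when each course began and ended. SCS can look like concomitant medication: Protocol 5.5.5 sends step-up therapy, including oral or injectable corticosteroids, to the Prior and Concomitant Medications CRF, and Protocol 6.4.1 has oral courses entered on the eCRF with start and end dates. The conversion table in SAP 5.2 also suggests that drug-coded records feed the derivation. SAP 5.1.3 is the only set of date rules for non-study medication, so a programmer might apply it by default.

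For classification, late end dates are harmless. For dose they lengthen short courses, and start rule 4a does the same within the treatment period. SAP section 4 says most patients lack sufficient follow-up, so annualisation would be common and would scale up any excess mg. The planned rank test gives no estimate in mg, so the summary statistics by arm are the only stated account of how much steroid was avoided. Those would be overstated.

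SAP 2.1 also appears to contradict rule 3 of 5.1.3.1 for wholly missing end dates.

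**Working it through.** **The plan's own figure.** SAP section 3 gives the tie-adjusted Wilcoxon formula. Inputs from Table 3.2: placebo 42.7/8.8/13.5/8.4/6.6/20.0%, fevipiprant 60/15/9/3/3/10%, two-sided alpha 0.025, power 90%, t = 0.5.
- Tie term: 1 - Σ((p+q)/2)³ = 0.85782
- Effect term: -0.11506, so 12 × 0.25 × 0.11506² = 0.03971
- N = (2.2414 + 1.2816)² × 0.85782 / 0.03971 = 268.1, or 134.04 per arm against 134 stated. Power at 134 per arm is 89.99%.

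The stated figure is reproduced and is not in dispute.

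**Size of the effect if imputed dates were used for dose.** Course lengths and daily doses are assumptions; the asthma plan leaves the dose blank.

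Unknown end day, true length L, course inside a 30-day month, start day s from 1 to 31 - L. Imputed length is 31 - s.

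| L (days) | Mean imputed length | Ratio to true |
|---|---|---|
| 3 | 16.5 | 5.5 |
| 5 | 17.5 (range 5 to 30) | 3.5 |
| 10 | 20.0 | 2.0 |
| 14 | 22.0 | 1.6 |

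Start rule 4a, L = 5, treatment starting on day d (1 to 26), true start s from d to 26: on-treatment length is s - d + 5. The mean of s - d is 25/3, so the mean length is 13.3 days, 2.7 times true.

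**Arm means.** With 5-day courses the mean rises by share missing × (3.5 - 1): 2.5% at a 1% share, 12.5% at 5%, 25% at 10%. Assigning 0/100/225/375/525/900 mg to the six categories gives a placebo mean of 8.8 + 30.4 + 31.5 + 34.7 + 180 = 285 mg. That becomes about 321 mg at 5% and 357 mg at 10%.

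**Rank test.** Simulation with the Table 3.2 distributions, those category values, 5-day courses at about 30 or 40 mg/day, 134 per arm, 2000 runs (Monte Carlo standard error √(0.9 × 0.1/2000) = 0.7 points):

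| Courses missing end day | Power, 30 mg/day | Power, 40 mg/day |
|---|---|---|
| 0% | 90.1% | 91.5% |
| 5% | 90.6% | 89.0% |
| 10% | 89.9% | 89.7% |
| 30% | 89.0% | 88.9% |

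A repeat with the same inputs and another seed gave 88.3% and 87.4% at a 30% share. A harsher check moves a share of all patients in the four middle categories straight to >600 mg in both arms. Power is then 90.0, 89.5, 88.8, 87.5 and 84.9% at shares of 0, 2, 5, 10 and 20%.

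**Annualisation.** At 40 mg/day the mean excess for one affected 5-day course is 12.5 × 40 = 500 mg, and 500 × 12/3 = 2000 mg with three months' follow-up. The true dose scales too: 200 mg becomes 800 mg. So the ratio for that record stays (200 + 500)/200 = 3.5. The 500 mg also ignores the last-contact cap and the on-treatment limit, which bind most often when follow-up is short.

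**Which source the documents point to.** Protocol 6.4.1 has patients record tablets taken morning and evening in the eDiary. Staff then count tablets, review the diary, ask about doses taken, and enter the result on the eCRF; dates accompany that dose. Protocol 5.5.6 and Table 6-1 treat OCS as rescue medication, and Table 6-1 gives it rows separate from concomitant medication. Protocol 5.1.2 asks patients to call no later than 48 hours after starting OCS. Protocol 8.1 requires full verification of primary-variable data, 8.2 has automatic discrepancy checks, and 8.3 sends queries for missing values.

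**The case for a change.** The strongest reply is that none of this is written into SAP 2.5. The eDiary and tablet counts are collected, but neither document says they supply the primary total or override eCRF dates. Injectable corticosteroids have no diary record at all. That is true, and it is what stands: the SAP leaves the source of SCS mg, and the limited purpose of 5.1.3, to be inferred.

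The date conflict also partly stands. SAP 2.1 treats undocumented end dates as continuing, which fits the exemption for ongoing records in 5.1.3.1. But SAP 2.4.2 lists ongoing and missing end dates separately, so a record not marked ongoing with a wholly missing end date falls under two rules. No result has been shown to turn on that narrow case.

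The argument about the mg summaries has some force, since they are the only description of steroid avoided. They are descriptive, though; no between-arm mg estimate is planned, and the exposure depends on partial dates surviving verification and queries. The 30-day secondary endpoint adds nothing, because SAP 2.7.2 and 2.7.3 rule out imputed data there.

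**Conclusion.** No change to the plan follows. The quoted rules and the arithmetic are right: applied to dose, the end-date rule would lengthen a short course with an unknown end day by 1.6 to 5.5 times on average (true length 14 down to 3 days). But the harm needs two conditions. The analyst would have to pass over the recorded dose in favour of daily dose times imputed duration, and partial SCS dates would have to be common. Nothing in either document directs the first, and the protocol's capture, query and verification steps make the second unlikely, although the documents give no frequency.

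The primary conclusion would hold even so. The rules do not depend on arm and the trial is blinded, so type I error is not at issue. Simulated power falls by roughly 1 to 4 points even with 30% of courses affected. At a 1% share the arm means would be about 2.5% too high.

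These sizes rest on assumed 5-day courses, 30-day months, 30 to 40 mg/day and the Table 3.2 distributions. The omission is a derivation detail that belongs in programming specifications and that analysts would settle sensibly from Protocol 6.4.1. The overlap between SAP 2.1 and rule 3 is a drafting slip.
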